7.2. Early Discontinuation of Study Intervention

Patients who prematurely discontinue study drug should still remain on study for scheduled visits and assessments and every effort should be made to obtain all protocol-specified assessments to avoid losing data that is needed to evaluate safety and efficacy. The assessments for primary, secondary, and exploratory endpoints, including the MRI and facial photography, should be completed within 30 days of the study drug discontinuation. The reason for premature discontinuation of study drug administration should be recorded on the appropriate page(s) of the eCRF.

Study drug must be discontinued in case of progressing disease posing an unacceptable risk to the patient that requires immediate treatment. In such cases, the PI should contact the Sponsor and the PI and the Sponsor Medical Monitor will discuss and determine whether the patient should continue in the study.

Reasons for withdrawal from study drug may include, but are not limited to:

- Withdrawal of consent
- An AE, which, in the opinion of the PI (or designee), warrants the patient's discontinuation of study drug infusion; in the event of study drug withdrawal due to the occurrence of an AE, the Medical Monitor must be notified within 24 hours
- Non-compliance with study drug administration or other protocol procedures
- Prohibited concomitant medication
- Physician decision
- Pregnancy
- Study termination

A patient who is withdrawn from study drug, or patients who are randomized, but not dosed, for reasons not related to study drug or progression of TED may be replaced at the discretion of the Sponsor.

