7.3. Participant Discontinuation/Withdrawal from the Study

Patients who wish to withdraw completely from this clinical study should be encouraged to complete the EOS/ET visit. However, patients may withdraw consent to participate in this study at any time without penalty or loss of benefits to which the patient is otherwise entitled. Every reasonable effort should be made to determine the reason a patient withdraws prematurely, and

this information should be recorded on the appropriate page(s) of the eCRF. Patients may be withdrawn from the study for any of the following reasons:

- Withdrawal of consent
- Protocol non-compliance with protocol procedures
- Lost-to-follow-up
- Physician decision
- Study termination

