6.2 Missing or Inconclusive Data Handling

In general, safety data will not be imputed except for missing or partial dates. The early termination visit will be mapped to the closest scheduled week based on study day. If the patient already has a result in the closest scheduled week, then the early termination visit will be mapped to the next nominal week. Missing efficacy data will be imputed using Last Observation Carried Forward (LOCF) to Week 53 (Day 365). Unscheduled visits will not be carried forward; however, the early termination visit that are mapped to the closest nominal week will be carried forward until Week 53 (Day 365).

Every effort will be made to collect all data at specified times. For the SRC or other IAs, selected AE variables that are missing will be re-coded or imputed as the worst option possible. Missing Relationship to Study Treatment will be re-coded as Related.

CONFIDENTIAL

The contents of this document are confidential to [REDACTED]
Unauthorized use, disclosure, or reproduction is strictly prohibited.

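### SAP 6.2 gives an off-schedule assessment made after stopping study drug no route into LOCF, so Week 37 can be scored on an older reading when a later one exists

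*SAP*

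**What the plan says.** **SAP 6.2 (Missing or Inconclusive Data Handling).** Missing efficacy values are filled by LOCF up to Week 53. Two rules decide what may be carried:

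- "Unscheduled visits will not be carried forward". The rest of that sentence exempts the mapped ET visit, which is carried to Week 53.
- "The early termination visit will be mapped to the closest scheduled week based on study day". If that week already has a result, the ET visit moves to the next nominal week.

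No other off-schedule reading has a mapping rule. SAP 11.1 applies LOCF in the Efficacy Population to the primary endpoint.

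**Protocol 7.2 (Early Discontinuation of Study Intervention).** "Patients who prematurely discontinue study drug should still remain on study for scheduled visits and assessments". The primary, secondary and exploratory endpoint assessments, MRI and facial photography included, "should be completed within 30 days of the study drug discontinuation".

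**Protocol 7.3 and footnote t of the schedule.** The ET visit belongs to patients who leave the study, and it is not mandatory: "Patients who wish to withdraw completely from this clinical study should be encouraged to complete the EOS/ET visit".

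**Protocol 1.3 (Schedule of Activities).** There is no column for an assessment triggered by stopping study drug.

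**The concern.** The protocol asks for a set of endpoint readings soon after a patient stops drug. The SAP has no place for those readings unless they coincide with a scheduled visit or are entered as an ET visit. If they are entered as unscheduled, the exclusion in SAP 6.2 applies to them as written.

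The gap has consequences only for a patient who then has no scheduled or ET reading up to Week 37. LOCF passes over the latest reading and carries the one before it. A responder can be scored as a non-responder or the reverse, although the information to score the patient on the latest reading was collected.

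The same Week 37 value also selects the eye followed at every visit in the either-eye responder analyses (SAP 6.1), so an outdated value there affects more than one table.

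**Working it through.** **1. The plan's own figure.** Inputs from Protocol 9.5 and SAP 4: 16 pooled LASN01 v 8 placebo, response rates 65% v 15%, one-sided Fisher's exact test, alpha 0.10.

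Power = Σₐ Σ_b Bin(a; 16, 0.65) × Bin(b; 8, 0.15) × 1[Fisher p(a, b) ≤ 0.10] = 81.8%, against about 81% stated. With a placebo rate of 10% it is 89.7%, against about 90% stated. Both reproduce, so the same test and sample sizes are used below.

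**2. How often a scheduled visit already meets the 30-day target.** Proptosis is scheduled on Days 29, 57, 85 and so on to Day 337 (every 28 days), then on Day 365.

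- From any stop day between Day 1 and Day 337, the next nominal proptosis visit is at most 28 days away, inside the 30 days.
- With one visit at its early window edge and the next at its late edge (±4 days each), the gap can reach 28 + 4 + 4 = 36 days.
- MRI is sparser: Weeks 9, 13, 29, 41, 53 and 73. Between Day 85 (Week 13) and Day 197 (Week 29), a stop on Days 86 to 166 has no nominal MRI within 30 days, because 197 − 30 = 167. A separate visit to complete the set is therefore plausible, and proptosis could be read then.

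An off-schedule proptosis reading is possible but not the usual case.

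**3. What the rule does when one occurs (invented dates).** A patient has a scheduled reading on Day 141 (Week 21), stops drug, is assessed on Day 160 as an unscheduled visit, and leaves before Day 169 without an ET visit. Under SAP 6.2 the Week 37 (Day 253) value is the Day 141 reading, which is 253 − 141 = 112 days old. The Day 160 reading, 253 − 160 = 93 days old, is not used. If the patient stays, the actual Week 37 reading is used. If the patient completes an ET visit, that reading is mapped and carried. The rule does no harm in either case.

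**4. What one re-scored patient is worth.** With r responders in total, one-sided p = Σ C(16, x) C(8, r − x) / C(24, r), over x at or above the observed active count.

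- 7/16 v 1/8 (r = 8): (11,440 × 8 + 12,870) / 735,471 = 104,390 / 735,471 = 0.142
- 8/16 v 1/8 (r = 9): (12,870 × 8 + 11,440) / 1,307,504 = 114,400 / 1,307,504 = 0.0875

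Other boundary pairs behave the same way:

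| Placebo responders | Active responders: p | One fewer active: p |
|---|---|---|
| 0/8 | 6/16: 0.0595 | 5/16: 0.1028 |
| 1/8 | 8/16: 0.0875 | 7/16: 0.1419 |
| 2/8 | 10/16: 0.0965 | 9/16: 0.1557 |

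On the percentage scale, one patient is 1/16 = 6.25 points in the pooled active group (6.25/50 = 12.5% of the assumed 50-point effect), and 1/8 = 12.5 points in placebo or in one dose arm.

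**5. Illustration on power.** The number affected is an assumption, shown over 0 to 2. Moving active patients from responder to non-responder changes power from 81.8% (none) to 71.7% (one) or 59.1% (two). Moving one placebo responder to non-responder instead gives 93.8%. The effect can go in either direction.

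**The case against.** **The documents do not say that the reading is discarded.** A reader might infer that the SAP throws away an assessment the protocol requires. The documents do not support that. Neither classifies the assessment as unscheduled, the case report form labels are not visible, and Protocol 7.2 says only that it should be completed. On a 28-day proptosis schedule it can usually be done at a scheduled visit, where it counts. This stands.

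**The harm needs several conditions together.** The patient must stop drug before Week 37, be assessed off-schedule, have the visit recorded as unscheduled, have no later scheduled or ET reading up to Week 37, and differ in responder status between the two readings. This stands, and it is why the event is probably uncommon.

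**The direction is not established.** A reader might also infer that patients who worsen are kept as responders, which would favour LASN01. Protocol 7.2 does say "Study drug must be discontinued in case of progressing disease posing an unacceptable risk to the patient", but it also lists withdrawn consent, adverse events, non-compliance, prohibited medication and pregnancy among the reasons for stopping. The attrition reported in SAP 1 and 16 is consent withdrawal and refusal to re-consent, not worsening. An omitted reading could be better than the one before it, and an error in a placebo patient works the opposite way to the same error in an active patient.

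**Observed-data analyses help, in part.** SAP 16 adds them for all proptosis and CAS tables, although SAP 11.1 says only that one may be run for the primary endpoint. They remove the outdated value from Week 37, but they do so by dropping the patient; the later reading is still unused there.

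**The p-values are boundary cases** and would apply to any single re-scored patient. That is correct. They show how sensitive the test is, not how often the problem arises.

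**Conclusion.** The concern holds in a conditional form. SAP 6.2 and Protocol 7.2 are not joined up: an off-schedule post-discontinuation reading recorded as unscheduled cannot enter LOCF. A patient with no scheduled or ET reading after it up to Week 37 is scored on an older on-treatment value.

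The number affected cannot be taken from the documents and may be zero, and the sign of any bias is not fixed. The reason to act is the sample size: with 16 v 8 patients, one changed responder status can move the primary p-value across 0.10 (0.142 v 0.0875). This rests on the planned group sizes and on the visit being labelled unscheduled, which neither document confirms or rules out. It is a gap to close in the SAP. It is not evidence that the primary result is biased.

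**What to change.** Amend SAP 6.2 so that the Protocol 7.2 post-discontinuation assessment is exempt from the unscheduled-visit exclusion, with these rules:

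1. Assign it to the closest nominal week if that week has no reading.
2. If that week already has a scheduled reading, keep the scheduled reading for that week.
3. If the assessment is later than the patient's last scheduled or ET reading, use it as the value carried forward to later missing visits.
4. Keep the exclusion for every other unscheduled reading.

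In the invented example, Day 160 is 9 days from Day 169 and 19 days from Day 141. It would be assigned to Week 25 and carried to Week 37.

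The cost is one more derivation flag and a short addition to the text; no new data are needed. Because the sponsor's clinical team has been unmasked (SAP 16), the still-masked CRO statisticians should specify the rule before database lock.

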6.2.1 PARTIAL OR MISSING DATES

Partial or missing dates required to identify treatment-emergent or concomitant data will be imputed.

For partial or missing start and end dates of AEs and concomitant medications, the following rules apply:

Partial or Missing Start Dates:

- Missing Day Only: Impute as the 1st of the month, unless the month and year match the first dose date, then impute the day of the first dose.
- Missing Day and Month: Impute as January 1st, unless the year matches the first dose year, then impute the day and month of the first dose.
- Completely Missing Date: Impute as the first dose date unless the end date is on or before the first dose date; in that case, impute as January 1st of the end date's year.

Partial or Missing End Dates:

- Missing Day Only Impute as the last day of the month, unless the month and year match the last dose date, then impute the day of the last dose.
- Missing Day and Month: Impute as December 31st, unless the year matches the last dose year, then impute the day and month of the last dose.
- Ongoing Flag Missing or "Yes": Do not impute the end date unless a death date is available; then impute as the death date.
- Ongoing Flag "No": Impute the missing end date as the last dose date.
- Lost to Follow-Up or Withdrawal Without End Date: Use the last known participation date as the end date.
- Imputed Date After Death Date: Set the end date equal to the death date.

Original dates will be displayed in data listings, and imputed dates will be used only for derivations (e.g., study day, treatment-emergent status).

6.2.2 DEFINITION OF BASELINE

Baseline will be defined as the last available, non-missing observation before the first study drug administration. In general, "Unknown," "Not Done," "Not Applicable," and other classifications of missing data will not be considered when calculating Baseline observations. However, valid categorical observations will be considered for Baseline calculations. In addition, non-missing results from unscheduled assessments before the first study drug administration may also be considered in the calculation of Baseline observations.

CONFIDENTIAL

The contents of this document are confidential to [REDACTED]
Unauthorized use, disclosure, or reproduction is strictly prohibited.

6.3 Data Analysis Conventions

Ora will perform all data analyses described in this SAP using [REDACTED]. Outputs will be provided in RTF for tables and figures, and in PDF for tables, listings, and figures (TLFs) in landscape orientation. Each formal TLF deliverable will include three combined PDF files, one for each of the output types.

Data will be summarized and listed separately. Continuous variables will be summarized using the number of patients (n), mean, standard deviation (SD), median, minimum, and maximum. Additionally, coefficient of variation (CV%), geometric mean and geometric CV% will be provided for PK concentrations and parameters (except for T_{max}). Values of 0 will be considered missing when calculating the geometric means. Categorical data will present counts and percentages within each category. Standard Error (SE) may be added to continuous efficacy outputs for Total CAS. Individual patient data listings will also be produced. For all other parameters except for PK concentrations and PK parameters, minima and maxima will retain the same precision as raw values; means and medians will have one additional decimal place; SDs will have two additional decimal places. For PK concentrations and parameters except n, all other descriptive statistics will be presented with the same number of significant digits as raw PK concentrations (3 significant figures). Percentages will be rounded to one decimal place (e.g., XX.X%). Differences between active treatment and placebo will be calculated as Active – Placebo, and change from baseline as Follow-up Visit – Baseline.

Unless otherwise specified, all statistical tests will be one-sided at a significance level of $\alpha=0.1$. Confidence intervals (CIs) for differences between treatment arms will be two-sided at 95% confidence unless stated otherwise. All p-values will be rounded to four decimal places; p-values less than 0.001 will be shown as "<0.001," and those greater than 0.9999 as ">0.999."

Summaries will be presented by treatment arm, including 300 mg, 600 mg, pooled treatment group (300 mg and 600 mg) for efficacy, placebo arm, [REDACTED] and, where appropriate, by visit and eye (study eye and either eye). Where possible, p-values will be displayed for comparisons of relevant active treatment groups to placebo; [REDACTED]. Listings will be presented by patient number, treatment arm, visit, time point, and parameter as applicable based on enrolled patients unless otherwise specified.

Masked SRC and masked IA outputs will generally reference the following 3 treatment groups unless otherwise specified in the shells:

CONFIDENTIAL

The contents of this document are confidential to [REDACTED].
Unauthorized use, disclosure, or reproduction is strictly prohibited.

- Treatment-Naïve group (pooled LASN01 300 mg, LASN01 600 mg, placebo)
- [REDACTED]
- All Patients

Unmasked IAs, topline, and final analysis outputs will generally reference 4 arms (LASN01 300 mg, LASN01 600 mg, placebo, [REDACTED]) for dispositional and safety outputs unless otherwise specified in the shells.

The All Patients group (including patients from LASN01 300 mg, 600 mg, placebo, and [REDACTED]) will be presented for the IA and may be presented for the final output where indicated in the shells.

Safety tables for the final analysis will include the LASN01 300 mg, LASN01 600 mg, [REDACTED], placebo, and All Patients columns.

6.4 Adjustments for Multiplicity

As this is an early-phase proof-of-concept study, there is no strong control of the family-wise error rate ($\alpha = 0.1$), and there are no multiplicity adjustments for the primary or secondary efficacy endpoints.

7. Disposition of Patients

Patient disposition will be presented in terms of the number of patients who were randomized to masked study medication [REDACTED], with subcategories of treated patients. The number and percentages of patients will be summarized for the analysis populations including the Efficacy, Safety, PK, and PD Populations. Number and percentage of patients who completed the study and discontinued from the study will be summarized. Patients who are not discontinued from the study will be considered study completers. Number and percentage of patients who completed treatment and discontinued the treatments early will be summarized. Completing treatment will be based on the patients' most recent consented protocol version. Disposition will be summarized by treatment arm, including LASN01 300 mg, LASN01 600 mg, placebo, [REDACTED], and overall for all patients. Percentages will be calculated using randomized (or enrolled patients) as the denominator unless otherwise specified.

The reasons for premature study discontinuation and treatment discontinuation will be summarized by treatment arm and overall for all discontinued patients. Percentages will be calculated using discontinued patients as the denominator. The reasons for study discontinuation that will be summarized include: Death, Lost to Follow-up, Physician Decision, Protocol non-compliance with protocol procedures, Study Termination, Withdrawal of Consent, and Other. The reasons for treatment discontinuation that will be

CONFIDENTIAL

The contents of this document are confidential to [REDACTED]
Unauthorized use, disclosure, or reproduction is strictly prohibited.

summarized include: Adverse Event, Non-compliance with study drug administration or other protocol procedures, Physician Decision, Pregnancy, Prohibited Concomitant Medication, Study Termination, Withdrawal of Consent, and Other. A patient listing will be provided that includes the date of and reason for premature study and treatment discontinuation.

The number and percentage of patients with any, major, or minor deviations, based on the “Severity” category collected from the Clinical Trial Management System (CTMS), will be summarized by treatment arm and overall for all patients. A patient listing will be provided that includes the date of the deviation, the deviation category, the deviation description, and CTMS variables (Reported to IRB and Severity). Severity of whether the deviation was judged to be important/major or minor will be determined by the clinical team and the sponsor before the database lock.

Listings will be provided that include informed consent date, protocol version, country of participation, meeting eligibility criteria or not, date of TED symptom onset, study eye, and exclusions from analysis populations with reasons for exclusions. Randomization, including previous teprotumumab, randomization date, randomization number, randomized treatment, and actual treatment, will be included within patient listings.

8. Demographic and Baseline Disease Characteristics

8.1 Demographic and Baseline Characteristic Variables

Demographics and baseline characteristics will be summarized by treatment arm and overall for all patients using continuous or categorical descriptive statistics based on the Safety Population.

The following demographic variables will be presented: age, age category, sex, ethnicity, race , and iris color for study eye and fellow eye.

The following baseline characteristics will be presented: baseline proptosis from Hertel for study eye and fellow eye, baseline Total CAS for study eye and fellow eye, height, weight, BMI, smoking history, duration of TED in months (Week 1 [Day 1] Date – Onset of TED symptoms), duration of Graves’ Disease in years (Week 1 [Day 1] Date – Graves diagnosis date), history of teprotumumab response, country of participation, free triiodothyronine, free thyroxine, thyroid stimulating immunoglobulin (TSI), and thyroid stimulating hormone (TSH).

Patient listings that include all demographic variables (year of birth, age, sex, childbearing potential, race, ethnicity, and iris color) will be provided. Baseline characteristics can be found on their respective listings.

CONFIDENTIAL

The contents of this document are confidential to [REDACTED]
Unauthorized use, disclosure, or reproduction is strictly prohibited.

9. Medical History, Medications, and Procedures

Medical history and medication listings will be generated separately for ocular and non-ocular data. Prior and concomitant procedures will be listed.

The medical history will be coded using the Medical Dictionary for Regulatory Activities (MedDRA) version as specified in the Data Management Plan (DMP). Listings of ocular and non-ocular medical history will be provided.

9.1 Prior and Concomitant Medications

Prior and concomitant medications will be coded using World Health Organization Drug Dictionary (WHODrug), with the version specified in the DMP.

Prior medications are those with an end date before the initiation of the study drug. Concomitant medications are those taken (1) before initiation of study drug administration and continuing after the first administration, or (2) at any time following the first administration of the study drug.

Both prior and concomitant medications will be listed. Ocular and non-ocular outputs will be generated separately.

A separate listing will be presented for current TED treatments.

